10.1.8. Source Documents

Source documents provide evidence for the existence of the participant and substantiate the integrity of the data collected. Source documents are filed at the investigator site.

Data reported on the CRF or entered in the eCRF that are from source documents must be consistent with the source documents or the discrepancies must be explained. The investigator may need to request previous medical records or transfer records, depending on the study. Also, current medical records must be available.

In this study, the CRF will serve as the source document. A document must be available at the investigative site that identifies those data that will be recorded on the CRF and for which the CRF will be the source document.

Definition of what constitutes a source document and its origin can be found in the Source Document Locator, which is maintained by the sponsor or sponsor's designee (Pfizer).

Description of the use of the computerized system is documented in the Data Management Plan, which is maintained by the sponsor.

The investigator must maintain accurate documentation (source data) that supports the information entered in the CRF.

The sponsor or designee will perform monitoring to confirm that data entered into the CRF by authorized site personnel are accurate, complete, and verifiable from source documents; that the safety and rights of participants are being protected; and that the study is being conducted in accordance with the currently approved protocol and any other study agreements, ICH GCP guidelines, and all applicable regulatory requirements.

10.1.9. Study and Site Start and Closure

The study start date is the date of the first participant's first visit. The sponsor designee reserves the right to close the study site or terminate the study at any time for any reason at the sole discretion of the sponsor, including (but not limited to) regulatory authority decision, change in opinion of the IRB/EC, or change in benefit-risk assessment. Study sites will be closed upon study completion. A study site is considered closed when all required documents and study supplies have been collected and a study -site closure visit has been performed.

The investigator may initiate study -site closure at any time upon notification to the sponsor or designee (Pfizer) if requested to do so by the responsible IRB/EC or if such termination is required to protect the health of study participants.

Reasons for the early closure of a study site by the sponsor may include but are not limited to:

- Failure of the investigator to comply with the protocol, the requirements of the IRB/EC or local health authorities, the sponsor's procedures, or the ICH GCP guidelines;
- Inadequate recruitment of participants by the investigator;
- Discontinuation of further study intervention development.

If the study is prematurely terminated or suspended, the sponsor shall promptly inform the investigators, the ECs/IRBs, the regulatory authorities, and any CRO(s) used in the study of the reason for termination or suspension, as specified by the applicable regulatory requirements. The investigator shall promptly inform the participant and should assure appropriate participant therapy and/or follow-up.

Study termination is also provided for in the clinical study agreement. If there is any conflict between the contract and this protocol, the contract will control as to termination rights.

10.1.10. Publication Policy

Publication by the clinical study site(s) of any data from this study must be carried out in accordance with the Clinical Site Agreement.

10.1.11. Sponsor's Medically Qualified Individual

The sponsor will designate a medically qualified individual (MQI, also known as the medical monitor) to advise the investigator on study-related medical questions. The contact information for the study medical monitor is documented in the Study Team Contact List located in the ISF or equivalent.

Participants are provided with a Pfizer study information card at the time of informed consent which includes contact information for their investigator in case of study-related medical

questions. The study information card contains, at a minimum, (a) study number, (b) participant's study identification number, and (c) principal investigator contact information.

090177e19fcc12ed\Approved\Approved On: 30-Jan-2024 19:45 (GMT)

10.2. Appendix 2: Clinical Laboratory Tests

The following safety laboratory tests will be performed at times defined in the [SoA](#) section of this protocol. Additional laboratory results may be reported on these samples as a result of the method of analysis or the type of analyzer used by the clinical laboratory, or as derived from calculated values. These additional tests would not require additional collection of blood. Unscheduled clinical laboratory measurements may be obtained at any time during the study to assess any perceived safety issues.

Clinical laboratory tests should be performed prior to KAN-101/PBO infusion when applicable.

Table 3. Protocol Required Safety Laboratory Assessments

Hematology	Chemistry	Urinalysis	Other
Hemoglobin	Urea and creatinine	Local dipstick:	At screening:
Hematocrit	eGFR	pH	FSH ^d
RBC count	Glucose (fasting)	Glucose (qual)	Pregnancy test
Platelet count	Calcium	Protein (qual)	(β-hCG) ^e
WBC count	Sodium	Blood (qual)	HBsAg and HBcAb.
Total neutrophils (Abs, %)	Potassium	Ketones	HBsAb and HBV
Eosinophils (Abs,%)	Chloride	Nitrites	DNA as reflex tests
Monocytes (Abs,%)	Total CO ₂ (bicarbonate)	Leukocyte esterase	Hepatitis C antibody
Basophils (Abs,%)	AST, ALT	Laboratory:	and HCV RNA as reflex test
Lymphocytes (Abs,%)	Total and direct bilirubin	Microscopy and culture ^c	HIV
PT	Alkaline phosphatase		HLA genotype and
aPTT ^a	Uric acid		CeD serology (eg,
INR ^a	Albumin		HLA DQ2.5 and HLA
	Total protein		DQ8 testing ^f , tTG and
	Magnesium		DGP IgA/IgG ^g)
	Amylase		
	Lipase		
	Phosphorus		
	hsCRP ^b		

- aPTT and INR tests are performed in Part A only.
- Part C only:** At times indicated in the SoA ([Section 1.3.3](#)).
- Only if UTI is suspected and urine dipstick is positive for nitrites or leukocyte esterase or both.
- For confirmation of postmenopausal status only.
- A serum pregnancy test is required at screening. Following screening, local urine testing will be standard for the protocol unless serum testing is required by local regulation or IRB/EC. Serum or urine β-hCG for female participants of childbearing potential.
- For re-screening, the HLA does not need to be repeated and CeD serology (the tTG and DGP antibody tests) should only be repeated if >3 months have elapsed from previous assessment.
- For tTG, a result of ≤ 10 U/mL will be considered negative or weak positive. For DGP, a result of <30 U/mL will be considered negative or weak positive.

The investigator must review the laboratory report, document this review, and record any clinically relevant changes occurring during the study in the AE section of the CRF.

Laboratory/analyte results that could unblind the study and have been collected for the purpose of the study will not be reported to investigator sites or other blinded personnel until the study has been unblinded.

10.3. Appendix 3: Adverse Events: Definitions and Procedures for Recording, Evaluating, Follow-Up, and Reporting

10.3.1. Definition of AE

AE Definition

• An AE is any untoward medical occurrence in a patient or clinical study participant, temporally associated with the use of study intervention, whether or not considered related to the study intervention.• Note: An AE can therefore be any unfavorable and unintended sign (including an abnormal laboratory finding), symptom, or disease (new or exacerbated) temporally associated with the use of study intervention.

Events Meeting the AE Definition

• Any abnormal laboratory test results (hematology, clinical chemistry, or urinalysis) or other safety assessments (eg, ECG, radiological scans, vital sign measurements), including those that worsen from baseline, considered clinically significant in the medical and scientific judgment of the investigator. Any abnormal test results that meet any of the conditions below must be recorded as an AE:
Is associated with accompanying symptoms.Requires additional diagnostic testing or medical/surgical intervention.Leads to a change in study dosing (outside of any protocol-specified dose adjustments) or discontinuation from the study, significant additional concomitant drug treatment, or other therapy.• Exacerbation of a chronic or intermittent preexisting condition, including an increase in either frequency and/or intensity of the condition.• New condition detected or diagnosed after study intervention administration, even though it may have been present before the start of the study.• Signs, symptoms, or the clinical sequelae of a suspected drug-drug interaction.• Signs, symptoms, or the clinical sequelae of a suspected overdose of either study intervention or a concomitant medication. Overdose per se will not be reported as an AE or SAE unless it is an intentional overdose taken with possible suicidal/self-harming intent. Such overdoses should be reported regardless of sequelae.

090177e19fcc12ed\Approved\Approved On: 30-Jan-2024 19:45 (GMT)

Events NOT Meeting the AE Definition

• Any clinically significant abnormal laboratory findings or other abnormal safety assessments that are associated with the underlying disease, unless judged by the investigator to be more severe than expected for the participant’s condition.• The disease/disorder being studied or expected progression, signs, or symptoms of the disease/disorder being studied, unless more severe than expected for the participant’s condition.• Medical or surgical procedure (eg, endoscopy, appendectomy): the condition that leads to the procedure is the AE.• Situations in which an untoward medical occurrence did not occur (social and/or convenience admission to a hospital).• Anticipated day-to-day fluctuations of preexisting disease(s) or condition(s) present or detected at the start of the study that do not worsen.

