2.2.3. Clinical Overview

KAN-101 was evaluated in a FIH Phase 1 study in patients with CeD on a GFD (KAN-101-01). This was a 2-part, multicenter study designed to examine the safety and tolerability of SAD (Part A) and MAD (Part B) of KAN-101. A total of 41 participants received at least 1 dose of KAN-101 (0.15 mg/kg, 0.3 mg/kg, 0.6 mg/kg, 1.2 mg/kg, and 1.5 mg/kg) during the study.

In Study KAN-101-01 administration of KAN-101 was effective at inducing T-cell tolerance:

- Three doses of KAN-101, administered 3 days apart, at 0.15, 0.3 and 0.6 mg/kg dose levels was effective in inducing T cell tolerance to gliadin. KAN-101 treated patients exhibited minimal change or a decrease in the gliadin-specific T-cell response following GC while placebo patients exhibited an increase in the gliadin-specific T-cell response following GC.
- KAN-101 also modified the immediate immune reaction upon ingestion of gluten by CeD patients in a dose-dependent manner. Patients treated with 3 doses of 0.6 mg/kg KAN-101, administered 3 days apart, exhibited lower median plasma IL-2 levels

within hours of GC compared to placebo or 0.15 and 0.3 mg/kg KAN-101 dose levels.

KAN-101 demonstrated an acceptable safety and tolerability profile after single and multiple doses at all dose levels tested in the KAN-101-01 study. There were no deaths, SAEs, Grade 3 TEAEs, or DLTs observed. TEAEs were consistent with CeD patients upon gluten ingestion (ie, nausea, emesis, abdominal pain, headache, and diarrhea). No clinically relevant trends were observed for changes in vital signs, physical examination, laboratory tests, or ECG results. There were no meaningful correlations between the frequency of TEAEs and study drug dose level. There was an increased frequency of subjects who experienced GI AEs in the total drug-treated group than in the placebo group. No MTD of KAN-101 was identified in KAN-101-01 and no meaningful safety differences were observed among treatment groups during the study.

Preliminary data from the KAN-101-01 study suggests rapid elimination with mean half-life ranging from 3.74 to 36.8 minutes across 0.15 mg/kg to 1.2 mg/kg doses, following single or repeat IV infusions of KAN-101. The mean KAN-101 maximum exposure (C_{max}) and systemic exposure (AUC) appeared to exhibit approximate dose proportionality across 0.15 to 1.2 mg/kg dose range. With repeat dosing, there was no accumulation of KAN-101 which was in concordance with the rapid elimination.

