2.3.1. Risk Assessment

Potential Risk of Clinical Significance	Summary of Data/Rationale for Risk	Mitigation Strategy
Study Intervention(s) [KAN-101 and PBO]		
Potential for exacerbation of gastrointestinal symptoms associated with CeD, which may include and are not necessarily limited to AEs of headache, dizziness, fatigue/lethargy, nausea, vomiting, abdominal pain, diarrhea, constipation, skin rash, and abdominal tenderness.	The potential risks are based on the mechanism of action of KAN-101 and other similar therapeutic investigational immunomodulatory therapies in CeD (Daveson et al, 2017; Truitt et al, 2019).	AEs and clinical laboratory results will be monitored on an ongoing basis and managed according to established standard of care.
Use of a placebo arm in Part B and Part C.	The use of a placebo represents a potential risk.	Participants who experience worsening of CeD may discontinue from the study and may receive SOC treatment at the investigator's discretion.
IV infusions will be administered over 30 minutes every 3 days during study treatment period.	IRR are known risks associated with IV infusions.	IRR will be monitored and specific guidance on acute and prophylactic treatment of IRRs and recommendations for future infusions of KAN-101 are provided in Appendix 9 .
Potential hypersensitivity reactions may occur and include skin reaction, mucosal tissue reaction, respiratory reaction, GI reactions, and CV reactions.	Similar to other biologic molecules.	Participants will be closely monitored on site for 4 hours post infusion for signs of any reaction.
KAN-101 is a liver targeting agent.	Although FIH Study KAN-101-01 and nonclinical data show that KAN-101 had no significant impact on the liver (eg, liver enzyme levels and histopathology), KAN-101's potential impact on liver enzymes will continue to be evaluated in the clinical setting.	Transaminase levels will be closely monitored and are included in safety laboratory assessments. Participants with ALT, AST, or ALP > 1.5 x ULN are not eligible for enrollment in KAN-101-02. Participants considered to have a potential case of Hy's law will lead to a cessation of clinical dosing and participant will be followed to resolution.
Study Procedures		

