8.2.1. Gluten Challenge

Participants are required to fast for at least 8 hours, except for water and any medications they might have previously been prescribed, prior to the study visits where GC are performed (see [SoA](#)).

- **Part A:** All eligible, enrolled participants will undergo GC at Day 15.
- **Part B:** All eligible, enrolled participants will undergo 1-day GC during run-in and at times as specified in the [SoA](#).
- **Part C:** All eligible, enrolled participants will undergo 1-day GC at times as specified in the [SoA](#).

In Part B, during run-in period: all participants must meet all inclusion criteria before commencement of GC except [Inclusion Criterion #5](#).

A qualified staff member will prepare the GC in bottles at times specified in the [SoA](#).

Participants will consume 9g of gluten protein PO in the clinic and avoid foods (only water is permitted) at least 30 minutes after completion of the gluten drink. The participant will be observed for at least 4 hours to monitor for hyperacute reactions requiring medical treatment and collection of biomarker samples.

Compliance with the GC is defined as completion of the entirety of the 9g GC, including container wash steps, within approximately 15 minutes. Participants will consume the GC on site under the observation of site staff.

Any symptoms associated with the GC should be recorded as AEs (See [Section 8.4](#)). Any AEs associated with the GC study assessment are separate to AEs related to study intervention (KAN-101/PBO).

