8.4. Adverse Events, Serious Adverse Events, and Other Safety Reporting

The definitions of an AE and an SAE can be found in [Appendix 3](#).

AEs may arise from symptoms or other complaints reported to the investigator by the participant (or, when appropriate, by a caregiver, surrogate, or the participant's legally authorized representative), or they may arise from clinical findings of the investigator or other healthcare providers (clinical signs, test results, etc).

The investigator and any qualified designees are responsible for detecting, documenting, and recording events that meet the definition of an AE or SAE and remain responsible to pursue and obtain adequate information both to determine the outcome and to assess whether the event meets the criteria for classification as an SAE or caused the participant to discontinue the study intervention (see [Section 7.1](#)).

During the active collection period as described in Section 8.4.1, each participant will be questioned about the occurrence of AEs in a nonleading manner.

In addition, the investigator may be requested by the sponsor to obtain specific follow -up information in an expedited fashion.

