8.4.6. Cardiovascular and Death Events

Not applicable.

8.4.7. Disease -Related Events and/or Disease -Related Outcomes Not Qualifying as AEs or SAEs

Not applicable.

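### Protocol 10.3.1 exempts expected celiac symptoms from the AE definition, 8.2.1 and 8.4.7 do not match it, and low-grade symptoms between an infusion and the Day 15 challenge are left to investigator judgment

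*Protocol*

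**What the plan says.** Four parts of the protocol bear on whether a celiac-type symptom becomes an AE.

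- Section 10.3.1, under events that do not meet the AE definition: "The disease/disorder being studied or expected progression, signs, or symptoms of the disease/disorder being studied, unless more severe than expected". The sentence goes on to tie expectation to the individual participant's condition.
- Section 10.3.1, under events that do meet it: "Exacerbation of a chronic or intermittent preexisting condition, including an increase in either frequency and/or intensity of the condition".
- Section 8.2.1: "Any symptoms associated with the GC should be recorded as AEs". There is no severity qualifier, and the sentence points to Section 8.4.
- Section 8.4.7, headed "Disease -Related Events and/or Disease -Related Outcomes Not Qualifying as AEs or SAEs", is marked not applicable.

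On the drug's profile, Section 2.2.3 says of the first-in-human study that "TEAEs were consistent with CeD patients upon gluten ingestion (ie, nausea, emesis, abdominal pain, headache, and diarrhea". The first risk listed in Section 2.3.1 is "Potential for exacerbation of gastrointestinal symptoms associated with CeD".

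Incidence and severity of TEAEs is the primary endpoint of Part A and a secondary endpoint of Parts B and C (Protocol Section 3).

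**The concern.** In most trials the disease-symptom exclusion is harmless boilerplate. Here the drug carries a gliadin peptide, and its anticipated adverse effects resemble the disease. An investigator who sees mild or moderate nausea or abdominal pain after an infusion can read 10.3.1 as saying that this is an expected symptom of celiac disease and not an AE. Another can read the exacerbation bullet and record the same event. The protocol gives no study-specific threshold for what counts as expected.

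At stake is the completeness of the TEAE count, and its consistency across sites. The question matters most in Part A, where TEAEs are the primary endpoint and cohorts are very small.

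**Working it through.** The documents give no figure for this point, so the check compares texts and symptom lists, followed by a short calculation of leverage.

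1. **Do the rules agree?** No. Section 10.3.1 creates a class of disease symptoms that are not AEs. Section 8.4.7, the body section reserved for such a class, says there is none. Section 8.2.1 records all GC symptoms but refers to Section 8.4, which says "The definitions of an AE and an SAE can be found in" Appendix 3. The specific rule therefore leads back to the definition that holds the exclusion. No sentence gives one rule precedence.

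2. **How far do drug effects and disease symptoms overlap?**
   - Section 2.3.1 lists ten AE terms for KAN-101 and ten for the GC: 10 of 10 are the same.
   - The five first-in-human TEAE terms (reading emesis as vomiting) are all in the GC list: 5 of 5.
   - Of those five, nausea, abdominal pain and diarrhea are among the five CDSD symptoms in Section 8.2.3.1: 3 of 5. Vomiting and headache are not.
   - Section 2.2.1's examples of GI symptoms of celiac disease include diarrhea and abdominal pain: 2 of 5.

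   The overlap is large but not complete.

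3. **Which rule applies when?** For symptoms associated with a GC, 8.2.1 applies directly, and all three SAPs plan a separate summary of GC-related TEAEs (Part A SAP 6.1; Part B and Part C SAPs 6.6.1). For symptoms after an infusion and before the Day 15 GC, 8.2.1 is silent and the Appendix 3 definition governs. In Part A this interval is the dose-escalation review period (Protocol 4.1.1.1.2 and 6.6.1), and it has its own TEAE summary (Part A SAP 6.1).

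4. **Can the analysis repair a gap?** No. The SAPs classify a recorded AE as a TEAE by its start date alone (Part A SAP 3.1; Part B and Part C SAPs 3.5.1) and do not impute missing safety data (5.3).

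5. **Leverage of one participant.** If a participant's only TEAE goes unrecorded, incidence in that group of n moves by 1/n:
   - Part A cohort of 3: 1/3 = 33.3 points; of 6: 1/6 = 16.7 points.
   - Part B group of 4: 1/4 = 25.0 points.
   - Part C group of 26: 1/26 = 3.8 points.

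   This measures sensitivity. It does not estimate how often omission happened, which the documents do not show.

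**The case against.** The strongest reply is that, read as a whole, the protocol leans toward recording.

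- Section 8.2.1 is specific, and the risk table already calls GC symptoms AEs. This stands. A general appendix bullet is unlikely to override it, so GC symptoms are mostly settled.
- For post-infusion symptoms, the exacerbation bullet covers any rise in frequency or intensity. Participants have also followed a gluten-free diet for at least 12 months, so new vomiting without gluten is not obviously expected for that person. The risk table speaks of AEs, and Appendix 10 supplies CTCAE grades for GI terms from Grade 1 upward. This also stands as a narrowing argument. It does not close the gap, because both the exacerbation bullet and the qualifier in the exclusion still ask the investigator what was expected.
- Event-triggered DSMB review in Parts B and C starts at Grade 3, which the severity qualifier would readily catch. That is fair. But the Part A escalation decision uses all AEs seen in the window (Section 6.6.1), and the DLT definition includes prolonged Grade 2 events (Section 4.1.1.1.1).
- CRF completion guidance sits in a separate document (Section 10.1.7) and may already have settled the matter. It is not available here, so this remains open.

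A reader might go further and infer that the bullet undermines the comparison between parts that led to the redesign. The documents do not support that. The amendment rationale compares Part B with Part A, Part C was created by the redesign, and the same Appendix 3 text applies to every part. Section 4.2 also shows that AEs after dosing were being recorded in Part B.

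**Conclusion.** The inconsistency is in the current text and concerns the definition that feeds the TEAE endpoint. It should be corrected. Its practical reach is mainly low-grade symptoms between an infusion and the Day 15 GC. The direction would be toward under-counting. The conclusion assumes that no site instruction outside these documents already resolves it.

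The size cannot be computed, because the documents give neither symptom rates nor site practice. Three stronger readings should be resisted:

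- That the whole TEAE endpoint turns on which rule a site follows. The specific GC rule and the exacerbation bullet prevent that.
- That the drug's adverse effects are the same thing as celiac symptoms. Step 2 shows partial overlap with the disease descriptions. Section 2.3.1 also lists infusion and hypersensitivity reactions, and Part C adds orthostatic monitoring.
- That incidence shrinks in proportion to the share of events omitted. The summaries count participants with any TEAE. If each of k events is omitted independently with probability f (both assumed), a participant is still counted with probability 1 − f^k. At f = 0.5 that is 50% for k = 1 but 1 − 0.25 = 75% for k = 2.

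**What to change.** Add a study-specific exception to the 10.3.1 bullet: any symptom that starts or worsens after a study infusion or a GC is recorded as an AE, whether or not it is expected for celiac disease. Cross-refer to 8.2.1 and 8.4.7 so that the three passages state one rule, and repeat it in the CRF completion guidance. The cost is a sentence in each document and more low-grade AEs to record and tabulate.

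The June 2025 SAP versions cite study termination. If dosing has ended, find out from the site instructions and monitoring records which rule sites followed, and state it beside the TEAE tables. The daily CDSD entries from Day 1 to the Day 15 GC could help show where symptoms were reported without a matching AE. They do not cover every term and are not CTCAE-graded, so they would be a check on recording and not a substitute for it.
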